#### **5.1.4.2 Modified BILAG 2004**

The majority of BILAG As and BILAG Bs assigned via the scoring algorithms of the BILAG 2004 are considered a legitimate representation of clinically significant worsening disease activity; however, there is a feature within the BILAG-2004 Index Scoring algorithms that can result in an A or B assigned to a body system which had improved, and then remained at the ‘same’ level of improvement compared to previous visits. Items marked ‘same’ frequently warrant assignment of an A or a B category following the BILAG-2004 Index Scoring based on the BILAG principle of Intention-to-Treat. These are “false” A or B categories because they are not true worsening of disease activity but are due to unchanged or the same disease activity that has previously improved. These “false” A and B can only be determined and subsequently re-scored after a participant had completed a series of visits that define true state of SLE disease activity.

The DACRT will differentiate “false” A and B scores from true clinically significant worsening by reviewing all BILAG-2004 Index scores for each participant’s visits. A modified BILAG-2004 Index Scoring Rules will be used. The modified BILAG rules and the review process and scoring as well as references used that justify the modification are detailed in a charter developed for this exercise.

#### **5.1.5 Physician global assessment**

A trained and certified Investigator will complete the PGA (see [Appendix G](#)). The PGA represents the physician’s overall assessment of average SLE disease severity on a VAS scale with 0 (no disease) to 3 (severe) disease activity over the last 4 weeks. The PGA for a given participant should be completed by the same physician whenever possible.

The PGA is a modification of the classic analogue scale in that it is anchored with numbers from 0 to 3 demarcating no, mild, moderate and severe disease. The number 3 indicates severe disease and is at the end of the scale. This refers to the most severe possible disease, and does not reflect the most severe seen in a particular participant, but the most severe disease ever seen in all SLE participants. Therefore, the line made by the physician along this scale should

virtually never get to this edge. Any disease rated greater than 2.5 is very severe. The range of moderate disease covers approximately 1.5 to 2.4. Mild disease falls below 1.5. The instrument is similar to a logarithmic scale, with greater distances or demarcations possible among more mild-moderate symptoms.

When scoring the PGA, the score from the previous visit should be reviewed and the mark should be moved relative to the score from the previous visit. This is a global assessment, factoring in all aspects of the participant's lupus disease activity. It should not reflect non-lupus medical conditions.

#### **5.1.6 Oral corticosteroid reduction**

Please refer to Section [7.7.3](#) for all information regarding steroid tapering.

#### **5.1.7 Systemic Lupus International Collaborating Clinics/American College of Rheumatology Damage Index**

The SDI has been developed to assess irreversible damage in SLE participants independently of its cause (SLE activity, therapy, comorbidities) but occurring after disease onset (see [Appendix K](#)). Damage, i.e., irreversible impairment since onset of SLE is usually defined as a clinical feature that has to be continuously present for at least 6 months to score. In addition, some irreversible events such as MI or a cerebrovascular accident score as damage on their occurrence. Briefly, damage is defined for 12 organ systems; peripheral vascular, ocular, neuropsychiatric, renal, pulmonary, cardiovascular, gastrointestinal, musculoskeletal, skin, endocrine (diabetes), gonadal, and malignancies. Damage over time can be stable or increase, to a maximum of 45 points, however there should be no decrease in the number of points ([Schwartz et al, 2009](#)).

#### **5.1.8 Cutaneous Lupus Erythematosus Disease Area and Severity Index inflammatory disease activity**

The CLASI is a validated index used for assessing the cutaneous lesions of SLE and consists of 2 separate scores: the first summarises the inflammatory activity of the disease; the second is a measure of the damage done by the disease (see [Appendix L](#)). The activity score takes into account erythema, scale/hypertrophy, mucous membrane lesions, recent hair loss, and non-scarring alopecia. The damage score represents dyspigmentation, scarring/atrophy/panniculitis, and scarring of the scalp. Participants are asked if their dyspigmentation lasted 12 months or longer, in which case the dyspigmentation score is doubled. Each of the above parameters is measured in 13 different anatomical locations, included specifically because they are most often involved in cutaneous lupus erythematosus (CLE). The most severe lesion in each area is measured.

### 5.1.9 Joint count

The swollen and tender joint count is based on left and right shoulder, elbow, wrist, metacarpophalangeal (MCP) 1, MCP2, MCP3, MCP4, MCP5, proximal interphalangeal (PIP) 1, PIP2, PIP3, PIP4, PIP5 joints of the upper extremities and left and right knee of the lower extremities. Conventionally, an active joint for the SLEDAI-2K calculation is defined as a joint with pain and tenderness and at least 1 of the following (warmth, erythema, swelling, or effusion) (Merrill, 2014). However, in this study an active joint for the joint count assessment is defined as a joint with tenderness and swelling only. Each of 28 joints will then be evaluated separately for tenderness (by palpating the joint) and swelling. Joints with intra-articular injection within 4 weeks are not evaluable for the assessment.

The joint count assessment will include questions regarding limitation of range of movements and effects of joint symptoms on basic and functional ADLs.

The joint counts must be performed by an assessor with experience in performing these assessments; see Section 5.1.1 for details.

### 5.1.10 Lupus Low Disease Activity State

A conceptual definition of LLDAS is 'a state, which if sustained, is associated with a low likelihood of adverse outcome, considering disease activity and medication safety' (Franklyn et al, 2016). As a composite endpoint employed in clinical trials, LLDAS is defined and measured by attaining all of the following 5 criteria:

- SLEDAI-2K  $\leq 4$ , with no activity in major organ systems (renal, CNS, cardiopulmonary, vasculitis) or fever;
- no new lupus disease activity compared with the previous assessment (SLEDAI-2K);
- a PGA  $\leq 1$  (scale 0–3);
- a current prednisone (or equivalent) dose  $\leq 7.5$  mg daily;
- standard maintenance doses of immunosuppressive drugs and approved biological agents (Golder et al, 2019). This criterion on immunosuppressive medications will be handled through the intercurrent event of RM.

## 5.2 Safety assessments

Key safety assessments are AEs, AESIs, vital signs, physical examination, safety laboratory tests, and ECGs. Safety assessments will be made at the times indicated in the Study Plan (see Table 3 for assessments to be performed at Screening, Table 4 for Treatment Period, and Table 5 for Follow-up). Participant-reported outcome assessments should be completed by the participant, unassisted by spouse, family members or friends.

### 5.2.1 Clinical laboratory assessments

All clinical laboratory tests will be performed in a central clinical laboratory at the times indicated in the study plans (Table 3, Table 4 and Table 5).

A serum pregnancy test (or serum FSH in postmenopausal females with menses absent for  $\geq 1$  year) will be performed at screening at the central laboratory. Urine pregnancy tests (for females of childbearing potential) will be performed at the site using a dipstick. Direct Coombs test samples will only be collected per Investigator's opinion at local laboratory and applicable BILAG assessment requirements for determining haemolytic anaemia. Abnormal safety laboratory results should be repeated as clinically indicated, as soon as possible (preferably within 24 to 48 hours).

Additional safety samples may be collected if clinically indicated at the discretion of Investigator. The date, time of collection will be recorded on the appropriate eCRF.

Every attempt should be made to redraw any missing safety laboratory tests, even if the participant has received the investigational medicinal product.

Investigator should make an assessment of the available results with regard to clinically relevant abnormalities. The laboratory results should be signed and dated and retained at centre as source data for laboratory variables. For information on how AEs based on laboratory tests should be recorded and reported, see Section 6.4.7.

In case a participant shows an AST or ALT  $\geq 3 \times \text{ULN}$  or total bilirubin  $\geq 2 \times \text{ULN}$  please refer to Appendix C. Actions required in cases of combined increase of Aminotransferase and Total Bilirubin – Hy's Law', for further instructions.

The following laboratory variables will be measured:

**Table 6 Clinical laboratory tests**

Screening
ANA, anti-dsDNA antibodies, anti-Sm antibody, anti-RNP, anti-Sjogren's Syndrome-related antigen A [SSA] and anti-Sjogren's Syndrome-related antigen B [SSB]
HbA1c in diabetic participants only
Peripheral blood B lymphocyte count (only for participants who received B cell depleting therapy prior to signing ICF, including but not limited to ocrelizumab, ofatumumab, atacicept, obituzumab, or rituximab)
BILAG-2004 associated laboratory tests analysed for all participants at screening (anticardiolipin, lupus anticoagulant, haptoglobin, and Coombs [Coombs will be performed at local laboratory as applicable per BILAG assessment requirements]) *
Hepatitis B surface antigen
Hepatitis B core antibody (reflex DNA testing if isolated HBc positive)
Hepatitis C antibody
HIV test

Clinical Study Protocol  
Drug Substance Anifrolumab (MEDI546)  
Study Code D3468C00003  
Version 4.0  
Date 19 May 2025

CK  
C3, C4, CH50 complement  
Urine protein/creatinine ratio  
SARS-Cov-2 RT-PCR  
QFT-G test

---

**Haematology (whole blood)**

---

Haematology/Haemostasis (whole blood)  
White blood cell count with differential  
Red blood cell count  
Haematocrit  
Haemoglobin  
Platelet count  
Mean corpuscular volume (MCV)  
Mean corpuscular haemoglobin concentration (MCHC)

---

**Serum Chemistry**

---

Calcium  
Chloride  
Potassium  
Sodium  
Aspartate transaminase\* (AST)  
Alanine transaminase\* (ALT)  
Alkaline phosphatase\* (ALP)  
Gamma glutamyl transferase (GGT)  
Blood urea nitrogen (BUN)  
Creatinine  
Bilirubin, total\* (reflexively fractionated if elevated)  
Glucose  
Albumin  
Creatine kinase (CK)  
\*Note for serum chemistry: Tests for AST, ALT, ALP, and total bilirubin must be conducted concurrently and assessed concurrently.

---

**Urinalysis**

---

Colour  
Appearance  
Specific gravity  
pH  
Protein dipstick  
Glucose  
Ketones  
Blood  
Bilirubin  
Microscopy including WBC/HPF, RBC/HPF, casts  
Urine creatinine and protein, urine protein/creatinine ratio

---

**Pregnancy Test**

---

Serum  $\beta$ -hCG (at screening only)  
Urine  $\beta$ -hCG (at every visit after screening, using a dipstick)  
Serum FSH (at screening only) in postmenopausal females with menses absent for  $\geq 1$  year

---

**Disease Evaluations**

---

SLEDAI-2K-associated laboratory tests (C3, C4, CH50 complement, anti-ds DNA, urine protein/creatinine ratio)  
Note: If central laboratory results are not available for SLEDAI 2K associated tests, samples should be redrawn one time within 14 days of the SLEDAI assessment date.

BILAG-2004 associated laboratory tests, including anticardiolipin, lupus anticoagulant, haptoglobin and Coombs (as applicable). Coombs will be performed at local laboratory as applicable per BILAG assessment requirements. \*

\* In order to avoid having to bring the participant back for a separate phlebotomy, the anticardiolipin, lupus anticoagulant, and haptoglobin blood specimen will be collected at the specified visits, however the blood will be stored at the central laboratory, and the analyses performed only if Investigator indicates that these tests need to be completed because of clinical suspicion of haemolytic anaemia or antiphospholipid syndrome. Direct Coombs test samples will only be collected per Investigator's opinion at local laboratory and applicable BILAG assessment requirements for determining haemolytic anaemia.

---

### **5.2.1.1 Laboratory assessments for cardiovascular risk assessments**

#### **Fasting lipid profile**

Participants will have a fasting lipid profile (high density lipoprotein cholesterol, low density lipoprotein cholesterol, and triglycerides) completed at times indicated in the Study Plan (Table 3, Table 4, and Table 5). Participants will be required to fast for at least 8 hours prior to this assessment (see Section 3.8.1).

#### **Immunology profile**

Participants will have tests to determine immunology profile (ANA, anti-Sm, anti-RNP, anti-SSA and anti-SSB), and quantitative immunoglobulins completed at times indicated in the Study Plan (Table 3, Table 4, and Table 5).

### **5.2.2 Physical examination**

Body height will be captured at screening only. Participants will be weighed at each study visit. Medically significant changes from the Screening physical examination will be recorded as AEs.

#### **5.2.2.1 Complete physical examination**

A complete physical examination will be performed at the visits specified in the Study Plan (Table 3, Table 4, and Table 5), and will include an assessment of the following: general appearance, head and neck, breast, respiratory, cardiovascular, abdomen, musculoskeletal/extremities, neurological, skin, lymph nodes, and thyroid.

#### **5.2.2.2 Focused physical examination**

The focused physical examination will include an assessment of the organ systems required to complete protocol-specified assessment tools (SLEDAI-2K, BILAG-2004, joint count, and CLASI). Additional assessments should be done as clinically indicated. Abnormal findings will be recorded as part of AE, SAE, AESI, or lupus activity, as appropriate.

#### **5.2.2.3 Cervical Cancer Screening Test (Pap Smear/HPV Test)**

Most cases of cervical cancer appear to be related to infection with papilloma virus. Because of the potential for viral reactivation due to blockade of the interferon pathway, we are

assessing cervical dysplasia in this study, although to date there has been no signal in the anifrolumab studies.

A Cervical Cancer Screening Test (Pap smear/HPV test which is in align with local practice) is required at screening in women who have not had their cervix surgically removed. If a Cervical Cancer Screening Test was performed within 2 years prior to screening with no documented malignancy (e.g., cervical intraepithelial neoplasia grade III [CIN III], carcinoma in situ [CIS], or adenocarcinoma in situ [AIS]) or no High-risk HPV was found, it does not need to be repeated. Abnormal Cervical Cancer Screening Test results received anytime within the 2 years prior to randomisations must be repeated to ensure eligibility. Please refer to [Appendix H](#) for guidance.

Participants should have a Pap Smear or HPV Test at the end of treatment per local standard of care, if possible, between Week 48 and Week 52, to ensure that there is no evidence of new cervical dysplasia. Since access to a Pap Smear or HPV Test may vary by county, the Sponsor recommends that local guidelines for obtaining Pap Smear or HPV Test in participants who have received immunomodulators or immunosuppressive treatment be followed. If a Pap Smear was performed at the EOT was not normal but showed no evidence of malignancy (e.g., CIN III, CIS or AIS), it should be repeated as per the participant's gynaecologists recommendation. If the participant's gynaecologist has recommended a repeat Pap Smear be performed at a specified interval, the Pap Smear should be obtained as recommended and the report provided in source document.

Females aged < 25 years, who have never been sexually active or have well documented HPV vaccination records may not require a cervical cancer screening test.

#### **5.2.2.4 Assessment of Cushingoid features**

Participants will be assessed for Cushingoid features at the visits specified in the Treatment Period Study Plan ([Table 4](#)). Features, such as moon face, buffalo hump, purple or violaceous striae, central obesity, hirsutism, acne, easy bruising, and fragile skin, will be captured separately to evaluate whether resolution of same can occur overtime with OCS reduction.

#### **5.2.2.5 ECG**

12-lead ECGs for all participants at all centers will be conducted at the centers using standardised ECG machines throughout the study. ECGs will be performed at Screening, Randomisation, and at Visit 14 (Week 52). ECGs will be obtained after the participant has been resting supine for at least 10 minutes prior to times indicated. All ECGs should be recorded with the participant in the same physical position.

Investigator will judge the overall interpretation as normal or abnormal. If abnormal, it will be decided as to whether or not the abnormality is clinically significant or not clinically

significant and the reason for the abnormality will be recorded on the eCRF, if the Investigator considers it clinically significant. Abnormal values shall not be recorded as AEs unless deemed clinically significant.

### **5.2.3 Vital signs**

Vital signs (ear temperature, blood pressure [BP], pulse rate, and respiratory rate) will be obtained at each visit. Vital signs should be taken with the participant resting in a sitting position. Temperature should be taken the same way at all visits for a given participant. Specific information on vital signs surrounding the infusion is included in Section 7.2.4 (Participant Monitoring/Procedures During and After Infusions).

### **5.2.4 Assessment of cardiovascular risk**

To understand the contribution of the chronic inflammatory response in SLE to dyslipidaemia (as a potential risk for accelerated subclinical arteriosclerotic cardiovascular disease) and the potential effects of anifrolumab treatment, both lipid (including LDL and HDL, triglycerides [see Section 5.2.1.1]) and inflammatory profiles will be obtained during the study. Various risk factors for atherosclerosis will be assessed as part of the participant demographics at screening according to the Adult Treatment Panel (ATP) III Guidelines. Current and previous concomitant medications received for cardiovascular indications should be collected and recorded.

### **5.2.5 Columbia Suicide Severity Rating Scale**

The C-SSRS (Appendix Q) is a unique, simple, and short method of assessing both behaviour and ideation that tracks all suicidal events, and provides a summary of suicidality (Posner et al, 2007). It assesses the lethality of attempts and other features of ideation (frequency, duration, controllability, reasons for ideation, and deterrents), all of which are significantly predictive of completed suicide.

The C-SSRS will be administered at all study visits by a trained rater. The trained rater will record the clinical observation on the scale, which will be used as the source document. If at all possible, the same individual should perform the assessment at each visit to reduce scoring variability. In the event the primary rater is not available, a designated back-up rater who meets the same qualifications may perform the C-SSRS. An Investigator physician will review completed C-SSRS responses on the day of assessment and document review within the source.

If a participant indicates having a rating of type 4 or 5 suicidal ideation on the C-SSRS suicidal ideation scale at any time since the previous visit when the C-SSRS was administered or indicates having had any suicidal behaviour since the previous visit, the participant should be referred to a mental health professional immediately. If the C-SSRS is administered by a

rater other than the Primary Investigator, it is recommended that the Primary Investigator confirms suicidal ideation before making a referral to mental health services; however this should not delay the referral.

## **5.2.6 Tuberculosis screening and monitoring**

### **5.2.6.1 Screening evaluation**

A blood test for TB will be done at screening using the IGRAs test (i.e., QuantiFERON® -TB Gold In-Tube [QFT-G] Test). Evaluation of all participants by QFT-G test will be performed by the central clinical laboratory, and chest imaging will be completed at screening. If an adequate (antero-posterior and lateral or per local standard of care) chest radiograph has been performed within 12 weeks prior to signing the ICF, it does not need to be repeated at the screening visit.

Compared to culture confirmed TB, overall, 87.6% of participants have a positive QFT-G result (Cellestis, 2005). The false negative rate in this setting appears to be over 12%. Further, the performance of the test in the setting of immunosuppressant drugs has not been evaluated. Nor has it been evaluated in individuals with medical conditions other than, or in addition to, latent TB or tuberculosis disease. The guide also states that “Medical treatments or conditions that impair immune functions can potentially reduce IFN- $\gamma$  responses and prevent detection of a specific response to the (secretory proteins) ESAT-6 and CFP-10 (the test stimulators)”.

Given the population to be enrolled in the SLE study, false negative tests are possible, so a chest radiograph is a relevant technique for detecting active pulmonary disease and minimizing potential risk to study participants.

### **5.2.6.2 Tuberculosis results from screening evaluations**

The procedures, and guidance for the evaluation of tuberculosis test results which must be performed based on the screening IGRA (i.e., QFT-G) test can be found in Section 3.1, Inclusion Criterion # 14.

### **5.2.6.3 Tuberculosis monitoring during the study**

All participants will be monitored for signs and symptoms of TB over the course of the treatment Period and at the follow up visits using the standardized New or Reactivated TB Surveillance Questionnaire. This questionnaire must be completed at every onsite visit prior to receiving study intervention. If a participant presents with signs/symptoms of TB or positive findings on the routine questionnaire, an IGRA TB (QFT-G) test should be administered.

**Participants, with indeterminate QFT-G results** for both the initial and retest **at Screening and for whom latent TB treatment is not warranted**, must undergo repeat retesting every 3 months for 6 months see study plan (Section 4.1).

- If the retest QFT-G result is still indeterminate at Week 24, no further retesting is required until the Week 52 QFT-G required for all participants.
- Positive QFT-G test result, the participant should be referred to a TB specialist. If a TB specialist is not available, the local country guidelines should be followed for further diagnostic work up and anti-TB treatment regimens. If no local guidelines exist for immunocompromised individuals, then USA guidelines may be followed. This should also be reported as an AESI.
- Negative QFT-G test result, then the participant does not need to continue TB testing outlined for participants with indeterminate results at screening.

All participants must undergo QFT-G testing from the central laboratory for TB at Week 52. For participants with negative QFT at baseline and no symptoms of active TB:

- Week 52 QFT-G negative: no further testing.
- Week 52 QFT-G indeterminate: repeat at Week 56. If negative no further testing, however if indeterminate repeat again at Week 60.
- Week 52 QFT-G positive: repeat QFT-G test as soon as possible. If confirmed follow recommendations for positive QFT-G results during study. If repeat test is indeterminate or negative follow recommendation for indeterminate results above. Consider referral to TB specialist.

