**Table 5 Study plan detailing the procedures during follow-up**

Visit Number	Follow-up Visit 1 a	Follow-up Visit 2 a	Details in Section
Study Week Procedure/Visit Window	8 weeks post last dose ±7D	12 weeks post last dose ±7D	
EQ-5D-5L, WPAI		X	5.3.1; 5.3.4
Complete physical examination, weight		X	5.2.2
Vital signs	X	X	5.2.3
Serum chemistry, haematology, and urinalysis	X	X	5.2.1
Urine pregnancy test in females of childbearing potential	X	X	5.2.1
PK blood sample	X	X	5.4.1
Immunogenicity blood sample d		X	5.4.3
TB questionnaire	X	X	5.2.6.3
SLEDAI-2K associated laboratory tests b	X	X	5.2.1
BILAG-2004 associated laboratory tests c	X	X	5.2.1
C-SSRS	X	X	5.2.5
BILAG-2004	X	X	5.1.4
CLASI	X	X	5.1.8
SLEDAI-2K	X	X	5.1.3
PGA	X	X	5.1.5
Joint count	X	X	5.1.9
Medical Resource Use Questionnaire	X	X	5.3.2
Assessment of AESIs	X	X	6.3; 6.6
Assessment of AEs/SAEs	X	X	6
Concomitant medications	X	X	7.7

AE = adverse event; AESI = Adverse Event of Special Interest; BILAG = British Isles Lupus Assessment Group; CLASI = Cutaneous Lupus Erythematosus; Disease Area and Severity Index; EQ-5D-5L = EuroQoL 5 dimensions; IFN = interferon; PD = pharmacodynamic; PGA = Physician's Global Assessment; PK = pharmacokinetic; SAE = serious adverse event; SLEDAI-2K = Systemic Lupus Erythematosus Disease Activity Index 2000; TB = tuberculosis; WPAI = Work Productivity and Activity Impairment; C-SSRS = Columbia Suicide Severity Rating Scale.

aFollow-up assessments are to be completed when participants complete the study (e.g., early termination or after the treatment period). Participants with early IMP discontinuation do not need to return for further safety follow-up assessments if they have been followed up for at least 12 weeks after the last dose during regularly scheduled clinical visits.

bSLEDAI-2K associated laboratory tests are C3, C4, CH50 complement, anti-ds DNA, urine protein/creatinine ratio. If central laboratory results are not available for SLEDAI-2K associated samples drawn on the date of visit, labs should be redrawn one time within 14 days of the SLEDAI assessment date.

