Participants should be monitored and a standardized TB questionnaire conducted at each required visit according to study plan. If a participant presents with signs/symptoms of TB or positive findings in the routine questionnaire, an IGRA [QFT-G] TB test should be administered.

The following guidelines must be followed based on TB test results:

- Participants with a negative IGRA [QFT-G] test result must be tested for TB again every 12 months from randomisation in both endemic and non-endemic regions.
- Participants testing positive at any time for TB must be referred to a TB specialist for evaluation. Active TB must be ruled out and initiation of treatment for latent TB prior to the first administration of study intervention in accordance with local standard of care.
- If a participant has an indeterminate IGRA [QFT-G] test result, he/she must be retested immediately using the same assay
  - (a) If in an endemic region\*, and the results upon immediate retest remain indeterminate, the participant must be referred to a TB specialist for evaluation (with assessment and treatment recommendation properly documented in source) before any further IMP administration. If warranted, appropriate latent TB treatment must be initiated prior to continued administration of IMP. If no latent TB treatment is warranted, the participant may continue to receive IMP without latent TB treatment, but must be administered a retest every 3 months for 6 months. If upon retest by the end of the 6 months, the result is indeterminate, the participant may continue in the study without latent TB treatment and continue with routine TB testing.
  - (b) If in a non-endemic region, and the results upon immediate retest remain indeterminate, the participant may continue in the study without latent TB treatment, but must be administered a retest every 3 months for 6 months. If, upon retest by the end of the 6 months, the result is indeterminate, the participant may continue in the study without treatment.

\* Endemic region as defined based on WHO lists of High Burden Countries (HBC) for TB and multi-resistant (MDR) TB. (See current list, [World Health Organization](#), 2020).

NOTE:

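### After an indeterminate or unconfirmed positive Week 52 QFT-G, Protocol 5.2.6.3 and 6.3.5 give different instructions, and Table 5 lists no QFT-G draw for the repeat

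*Protocol*

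**What the plan says.** **Protocol 5.2.6.3** calls for a central-laboratory QFT-G in all participants at Week 52. The actions that follow the result are limited in scope: "For participants with negative QFT at baseline and no symptoms of active TB". Within that group:

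- Indeterminate: "Week 52 QFT-G indeterminate: repeat at Week 56. If negative no further testing, however if indeterminate repeat again at Week 60". No immediate retest and no referral is mentioned.
- Positive: repeat as soon as possible. A confirmed positive goes to the rule for positive results during the study, which is referral. If the repeat is negative or indeterminate, the participant follows the indeterminate path. The bullet ends: "Consider referral to TB specialist".

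**Protocol 6.3.5**, the section on tuberculosis as an adverse event of special interest (AESI), sets rules by test result:

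- Indeterminate: "If a participant has an indeterminate IGRA [QFT-G] test result, he/she must be retested immediately using the same assay". In an endemic region, if "the results upon immediate retest remain indeterminate, the participant must be referred to a TB specialist for evaluation"; that referral is worded as coming before further dosing. Retests every 3 months for 6 months follow in non-endemic regions, and in endemic regions where latent TB treatment is not judged necessary.
- Positive: "Participants testing positive at any time for TB must be referred to a TB specialist for evaluation". There is no confirmation step.

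**Schedules.** Table 4 has a QFT-G row with entries at Weeks 12 and 24 (conditional, explained in a footnote), Week 52 and the early discontinuation visit. For Follow-up Visits 1 and 2, the only TB procedure in Table 5 is the "TB questionnaire".

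**The concern.** The two sections cover the same test result in the same participant. A site can comply with 5.2.6.3 and breach 6.3.5, or the reverse. The site's working schedule for the follow-up period does not show the repeat test that 5.2.6.3 requires.

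TB including latent TB is an AESI, and SAP 4.6.2.2 reports it as its own category. Apart from the conditional Week 12 and 24 retests, the Week 52 or early discontinuation sample is the only routinely scheduled QFT-G after screening. If sites retest at different times and refer under different rules, participants with the same result get different follow-up, and the record of conversions depends on which section was read.

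**Working it through.** The plan gives no figure to reproduce. The check is a comparison of the passages plus visit arithmetic.

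**1. Indeterminate at Week 52.**

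| Step | 5.2.6.3 | 6.3.5 |
|---|---|---|
| First retest | Week 56, 4 weeks later | Immediately |
| If still indeterminate | Week 60 | Every 3 months for 6 months |
| Specialist referral | None stated | Mandatory in endemic regions, tied to further dosing |

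The first row is a direct conflict: a single first retest cannot be both immediate and four weeks later.

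**2. Positive at Week 52.**

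| Situation | 5.2.6.3 | 6.3.5 |
|---|---|---|
| First positive | Repeat the test | Refer |
| Repeat positive | Refer | Refer |
| Repeat negative or indeterminate | Indeterminate path; consider referral | Referral already mandatory |

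The sections agree on a confirmed positive. They differ on whether a first or unconfirmed positive must be referred.

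**3. Visit timing.** The last dose is at Week 48 (Protocol 4.3). Follow-up visits are 8 and 12 weeks after it: 48 + 8 = Week 56 and 48 + 12 = Week 60. Both repeats in 5.2.6.3 therefore fall on existing visits, which already include blood sampling. Taking 3 months as 13 weeks, the 6.3.5 series counted from Week 52 falls at 52 + 13 = Week 65 and 52 + 26 = Week 78. Both are later than Week 60 even with the 7-day visit window, so these retests have no scheduled visit.

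**4. Schedule check.** Table 5 has no QFT-G row and no QFT-G footnote. Elsewhere the protocol does schedule conditional tests: Table 4 footnotes the Week 12 and 24 QFT-G and the HBV DNA tests. Table 4's QFT-G row refers to 5.2.6.1, the screening section, and its footnote refers to 6.3.5. Neither refers to 5.2.6.3, where the Week 52 rules sit.

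**5. Reporting.** In 5.2.6.3 a positive QFT-G is to be reported as an AESI. That sentence is written for participants indeterminate at screening, and the Week 52 rule sends confirmed positives to the recommendations for positive results during the study. In 6.3.5 a positive test without clinical or radiological work-up is not to be classified as latent TB but reported as test-positive. Whether work-up happens depends partly on the referral rule followed.

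The SAP's adverse event periods (4.6.2.1) end at last dose + 28 days and last dose + 84 days; later events are only listed. From the Week 48 dose, Week 56 is 8 × 7 = 56 days, Week 65 is 17 × 7 = 119 days and Week 78 is 30 × 7 = 210 days. If a site dates the event by the retest, a Week 56 finding falls in the treatment-plus-follow-up summary only, and a Week 65 or 78 finding falls outside both summaries.

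**The case against.** The best defence is that 5.2.6.3 is the specific rule for Week 52 and 6.3.5 the general one. Several clauses in 6.3.5 concern starting or continuing study drug and have no effect after the Week 48 dose, including the wording around the endemic-region referral. This stands in part. However, the immediate-retest requirement and the referral of anyone positive at any time are not tied to dosing, and 6.3.5 describes its testing as running through the follow-up period. Nothing in the protocol says that 5.2.6.3 overrides it.

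A reader might infer that the required repeats have no visit at all. The documents do not support that for Weeks 56 and 60: both visits exist and take blood. Table 5's TB questionnaire row also points to 5.2.6.3, and unscheduled visits and additional safety samples are allowed (4.4, 5.2.1). What is missing is the listed draw. Only the 3-monthly series in 6.3.5 lacks a visit.

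A reader might also infer that the two rules for a positive result exclude each other. They do not: a site can repeat the test and refer. The difference is mandatory against optional referral.

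Finally, the questionnaire at every visit can trigger a QFT-G, so Week 52 is not the only route to detecting TB. That is correct, but the questionnaire asks about signs and symptoms and is not a routine test for silent conversion.

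**Conclusion.** The inconsistency is real and limited. For baseline-negative participants without symptoms, the protocol gives two different timings for the first retest of an indeterminate Week 52 result, two different later paths, and two different strengths of referral for a first or unconfirmed positive. Table 5 omits the conditional draw that 5.2.6.3 requires.

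A reader might extend this to every participant because all are tested at Week 52. The 5.2.6.3 actions do not cover those who were positive or indeterminate at baseline or who have symptoms, so the conflict as described does not arise for them. A reader might also want a count of those affected. The documents give neither an indeterminate rate nor the number expected to be tested at Week 52, so none is offered; the conflict does not depend on one.

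No efficacy endpoint or inferential analysis is touched, and safety is summarised descriptively. The effect on AESI classification is a possibility that follows from the wording, not a demonstrated bias. The Week 65 and 78 dates assume that the 3-monthly series is counted from Week 52.

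**What to change.** Reconcile 5.2.6.3 and 6.3.5 into one stated rule for indeterminate and for positive Week 52 results, covering when the test is repeated, whether referral is mandatory, and how a positive test without work-up is reported. If the agreed rule includes any retest after Week 60, state who follows the participant and where the result is recorded. Add a conditional QFT-G row or footnote to Table 5 that matches the agreed rule, and point Table 4's QFT-G row to the section that holds it. The sponsor decides which rule stands; this review takes no position on that.

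The cost is protocol wording and one conditional table entry. Follow-up Visits 1 and 2 already draw blood, so repeats at those visits need no new visit; retests after Week 60 would need one only if the sponsor keeps them.
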